6 STATISTICAL ANALYSIS

Please refer to section 13 for an overview of tables (marked “T”), listings (“L”) and figures (“F”).

6.1 Summary Tables

All collected efficacy and safety assessments will be presented by means of descriptive statistics. If not detailed otherwise, the parameters listed below will be tabulated according to the different types of data. The number of subjects in the analysis population (N) and the number of subjects contributing to each particular summary (n) will be included in every presentation.

Where appropriate, results will be presented grouped by different subject characteristics, such as bleeding sites or surgery types, as well as in total.

- Binary data (whether or not an event has occurred): counts and proportions
- Count data (the frequency of an event in a set time period): rate (count per unit time)
- Continuous data (measurements on a continuous scale, including quasi-continuous variables): arithmetic mean, standard deviation, median, lower and upper quartile, minimum, maximum
- Scales data (Ordinal and Non-ordinal): absolute and relative frequencies
- Time-to-event data (how long it takes to observe the outcome of interest, e.g. the development of inhibitors to FVIII): time to event or last evaluation (censored data in case subjects are lost to follow-up) and event rate. These parameters might not be tabulated separately, but can be included as an inset into a Kaplan-Meier plot of the product-limit survival function estimates.

In addition this type of data can be shown in life-tables.

Additional descriptive and exploratory statistics, such as geometric means or confidence intervals, are included as appropriate. If not mentioned otherwise, confidence intervals are to be understood as two-sided, 95% confidence intervals.

Please refer to section 13 for a table of tables included in the statistical report.

6.2 Figures

Figures will always reference to the number of subjects contained in the analysis population and the number of observations represented in the graphic. Various types of graphs, including bar charts, scatter plots, line plots, Kaplan-Meier plots, and plots showing mean \pm standard deviation over time points will be used to illustrate the statistical outcome. Please refer to section 13 for a table of figures included in the statistical report.

6.3 Listings

For selected results, statistical summarization alone seems inappropriate, and listings will be presented to facilitate in-depth review of the data; these include:

- AE
- Reason for withdrawal

SAS datasets including individual subject data will be prepared. Datasets will be available on request, e.g. for an electronic submission according to CDISC /SDTM. Therefore no listings will be prepared for Section 16.4. Please refer to section 13 for a table of listings included in the statistical report.

6.4 Statistical Analytical Issues

The statistical analysis of the primary, secondary and safety endpoints is to be understood in the exploratory sense. Therefore no confirmative statistical analysis is planned.

6.4.1 Adjustments for Covariates

Not applicable.

6.4.2 Handling of Dropouts or Missing Data

In general, missing data values will not be imputed, except for the following:

- Body weight: In case of missing weight, the last available weight measurement will be used (last observation carried forward). Body weight will be estimated for the first exposure day: if body weight is not available on ED1 it will be estimated by linear interpolation between last available data before and after ED1.
- Date of birth: only month and year will be presented in listings.
- Age: calculations at screening and at ED1 in case of partially missing data:
 - If month and year available: “1” for day will be imputed
 - If month missing, but year available: “July” will be imputed
 - If month missing, but year available: “1st of July” will be imputed
 - no imputation otherwise
- Inhibitor measurement in the ITI study: In case inhibitor measurements have turned from positive to negative in the ITI sub-study and are missing at subsequent determinations of recovery and/or half-lives, they will be carried forward in order to facilitate the calculation of the number of ITI success criteria.
- Subjects who permanently switch to another FVIII product during their study participation, will be considered treatment failures, i.e. the efficacy will be imputed to be “none” for each haemostatic efficacy assessment after the switch in the efficacy analyses.

There will be two exceptions for subjects switching to another FVIII product during their study participation, and will thus **not** be considered treatment failures in the efficacy analyses:

- a) if the administration of another FVIII concentrate was due to an emergency situation,
- b) if the IMP was not available for the patient in time.

In either of these cases the efficacy will be considered a missing value with regard to *Human-cl rhFVIII*.

- Efficacy evaluation by the surgeon and the haematologist at the end of the surgery and on the last post-operative day (end of post-operative phase):
Subjects who switch to another FVIII product during a surgery will be considered treatment failures, i.e. the efficacy will be imputed to be “none” for all haemostatic efficacy assessment after the switch for this surgery. Exception: Not enough *Human-cl rhFVIII* study drug was available at the site; in this case the efficacy will be considered a missing value with regard to *Human-cl rhFVIII*.

A complete list of dropouts (subjects prematurely ending the study) will be presented, including the reason for premature discontinuation of the study and the duration of participation in terms of both, total days and exposure days.

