## Screening Visit:

Patients' parent(s)/legal guardian(s) will be informed about the study details and will be required to give their written informed consent before any investigations and assessments can be performed. The following will be documented/assessed:

- Check of inclusion- and exclusion criteria
- Demographics, including patient's blood type and FVIII inhibitor risk factors
- Medical history
- Vital signs
- Height
- Body weight
- Physical examination
- Safety laboratory parameters
- FVIII:C (CHR and OS assay)
- FVIII inhibitor screen
- Additional Health Economic Evaluation
- RNA expression analysis (optional)
- FVIII gene mutation analysis (mandatory, can be performed later during the study)
- Immunogenotyping (optional, can be performed later during the study): HLAtyping, immune response gene profiling, FVIII ethnic haplotype determination
- *In vitro* immunogenicity of FVIII products (optional)
- Epitope mapping (optional)

Name of Sponsor/Company: Octapharma AG, 8853 Lachen, Switzerland	
Name of Investigational Product:	Protocol Identification Code:
Human-cl rhFVIII	GENA-05
Name of Active Ingredient:	Date of Final Protocol:
Coagulation FVIII	01-Feb-2018

The Investigator will hand out the patient diary and instruct the patient/legal guardian how to document details of treatment with *Human-cl rhFVIII*, bleeds, AEs and concomitant medication. The patient/legal guardian will receive a sufficient amount of the study product for home treatment (in cooling boxes, if appropriate) and will be instructed on how to store and administer it. Details of home treatment (parents' home treatment training, the involvement of the general practitioner or a study nurse is documented).

Follow-Up Visits (every 3-4 EDs until ED 20):

The patients will visit the study site every 3-4 EDs until 20 EDs have been reached. At these visits, patients' body weight will be checked, and blood samples will be obtained for FVIII inhibitor screen and optionally RNA expression analysis (after a wash-out period of at least 2, preferably 3 days after the previous IMP administration). IMP injection is possible after blood sampling.

At these visits, the patient diary will be reviewed (any IMP injection, any bleed) in order to transfer data into the Case Report Form (CRF). The occurrence of AEs and changes in concomitant medication will be checked and documented.

Follow-Up Visits (every 10-12 EDs):

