## **1.2** Dose Rationale

*Human-cl rhFVIII* will be provided in single use vials containing a nominal potency of 250, 500, 1000 or 2000 International Units (IU) each of freeze-dried rFVIII concentrate to be reconstituted in 2.5 mL of water for injection (WFI). Full vials are to be injected, preferably - except for recovery investigations. *Human-cl rhFVIII* should be used for intravenous injection only (maximum infusion speed: 4 mL/minute).

The dose and frequency of treatment of Haemophilia A depend on the individual patients' needs. As the current study will be conducted in PUPs, who will most likely be infants or

Amended Study Protocol	CONFIDENTIAL	Version 05
No. GENA-05		01-Feb-2018

young children, and the recommendations in the published literature are controversial, no direct prophylactic dosing specifications are made, except that the starting dose should be 20-50 IU/kg BW. It is the Investigators' clinical judgement that will guide dose and frequency adjustments based on individual patients' needs.

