## **4 STUDY POPULATION**

## 4.1 **Population Base**

Male patients (mainly new-borns or infants, although no age limitation is given) with severe Haemophilia A (FVIII:C < 1%), without any previous FVIII concentrate treatment or any previous treatment with other FVIII-containing blood products will be enrolled into the study.

In total, 100 PUPs will be enrolled by approximately 40 centres from around the world.

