# 9.2.6 Handling of Missing Data

In general, missing data will not be imputed: calculations pertaining to person-year computations will be based on observed values only. Only in case of missing BW, the last available weight measurement will be used for calculating the dose per kg bodyweight (last observation carried forward).

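### Carrying the last measured weight forward in growing infants overstates IU/kg by a few percent at the usual weighing gaps; the SAP already interpolates at ED1 and should do so on every unweighed infusion day

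*SAP*

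**What the plan says.** SAP section 6.4.2 gives two rules for a missing body weight. In general, "In case of missing weight, the last available weight measurement will be used (last observation carried forward". At ED1 there is an exception: "if body weight is not available on ED1 it will be estimated by linear interpolation between last available data before and after ED1". Protocol section 9.2.6 has only the first rule and ties it to one use: "Only in case of missing BW, the last available weight measurement will be used for calculating the dose per kg bodyweight".

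Three other parts of the protocol decide how often the rule applies:

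- **Population (section 4.1).** Patients are "mainly new-borns or infants, although no age limitation is given".
- **Weighing.** Weight is checked at screening, at follow-up visits, at 3-monthly visits, at completion and before surgery. Early on, "The patients will visit the study site every 3-4 EDs until 20 EDs have been reached"; after that the spacing is 10-12 EDs, with 3-monthly visits alongside.
- **Home treatment (section 5.7.2).** Most treatment is given at home. The listed items for a home injection are timing, dose, batch and reason, with no weight.

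Section 1.2 adds "Full vials are to be injected, preferably", so the dose in IU can stay the same while the child gains weight.

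The SAP does not say whether the interpolated ED1 weight is used for dose per kg, or whether it is carried forward to later days. It plans no sensitivity analysis on the weight rule.

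**The concern.** Carry-forward is harmless for a quantity that fluctuates around a level. The weight of a growing infant does not. Between two weighings the last measured value is too low, so IU divided by it is too high. The errors all have the same sign and do not average out over infusions or patients. They are larger in faster-growing children and at longer weighing gaps, that is, with sparse dosing.

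Two kinds of output are exposed. The first is the set of IU/kg consumption tables for prophylaxis, on-demand treatment, ITI, bleeds and surgery. The second is less obvious. SAP section 5.1 counts a single day with a prophylactic dose above 50 IU/kg as a peak treatment moment, and section 9.1 uses the number of such moments as the treatment-intensity factor in the logistic and Cox models for inhibitor development. The recommended prophylactic range in protocol section 5.4 ends at 50 IU/kg, exactly at that cut-off, so a small upward error can reclassify a day.

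There is also a question of internal consistency. If ED1 uses an interpolated weight and an unweighed ED2 goes back to the older measured weight, the same dose in IU appears as a rise in IU/kg.

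**Working it through.** The plan states no figure on this point, so there is none to reproduce. The size has to be worked out from an assumed growth rate.

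**Inputs from the documents.** Visit spacing is 3-4 EDs up to ED 20, then 10-12 EDs, with 3-monthly visits. The smallest vial is 250 IU. The peak-treatment cut-off is above 50 IU/kg (SAP 5.1), and a relevant dose change is at least 30 IU/kg (SAP 3.4.2).

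**Assumption.** Constant relative growth g of 1, 2, 5 or 10% per month of 30.4 days, with infusions spread evenly over the gap. At zero growth every figure below is zero.

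**Overstatement under carry-forward.** The error is true weight / last measured weight − 1. At the end of a gap of D days it is (1+g)^(D/30.4) − 1. Averaged over the gap it is [(1+g)^(D/30.4) − 1] / [(D/30.4) × ln(1+g)] − 1. For D = 28 and g = 10%, the end-of-gap error is 1.10^0.921 − 1 = 9.2%, and the mean is 0.09175/0.08779 − 1 = 4.5%.

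Mean / maximum overstatement of IU/kg:

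| Weighing gap | 1% | 2% | 5% | 10% |
|---|---|---|---|---|
| 8 days (4 EDs, every other day) | 0.1 / 0.3% | 0.3 / 0.5% | 0.6 / 1.3% | 1.3 / 2.5% |
| 24 days (12 EDs, every other day) | 0.4 / 0.8% | 0.8 / 1.6% | 2.0 / 3.9% | 3.9 / 7.8% |
| 28 days (4 EDs, weekly) | 0.5 / 0.9% | 0.9 / 1.8% | 2.3 / 4.6% | 4.5 / 9.2% |
| 42 days (12 EDs, twice weekly) | 0.7 / 1.4% | 1.4 / 2.8% | 3.4 / 7.0% | 6.9 / 14.1% |
| 91 days (3-monthly only) | 1.5 / 3.0% | 3.0 / 6.1% | 7.7 / 15.7% | 15.7 / 33.0% |

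**Effect at the 50 IU/kg cut-off.** With overstatement k, true doses above 50/(1+k) are counted as above 50. For k = 5% this is 50/1.05 = 47.6 IU/kg; for k = 10% it is 50/1.10 = 45.5 IU/kg. One day is enough to qualify, so the maximum error matters here more than the mean.

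**ED1 to ED2, on the literal reading.** With W0 measured a days before ED1 and W1 measured b days after, the ED1 weight is W0 + (W1 − W0) × a/(a+b). At constant IU, the apparent rise when ED2 goes back to W0 is (ED1 weight)/W0 − 1. With b = 28 and growth of 1 / 2 / 5 / 10% per month:

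- a = 30 days: 1.0 / 2.0 / 5.0 / 10.3%
- a = 91 days: 3.0 / 6.2 / 16.1 / 34.6%

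**Example with assumed weights.** A child weighs 4.8 kg 60 days before ED1 and 5.8 kg 28 days after it, and receives 250 IU on ED1 and again on ED2, 7 days later. The implied growth is (5.8/4.8)^(30.4/88) − 1 = 6.8% per month, inside the assumed range.

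- ED1 weight: 4.8 + 1.0 × 60/88 = 5.48 kg, so 250/5.48 = 45.6 IU/kg.
- ED2, older weight carried forward: 250/4.8 = 52.1 IU/kg, a rise of 14% that crosses the cut-off if the dose is prophylactic.
- ED2, interpolated: 4.8 + 1.0 × 67/88 = 5.56 kg, so 45.0 IU/kg.
- ED2, ED1 estimate carried forward: 45.6 IU/kg, so no jump.

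**Dose-change rule.** A false change of 30 IU/kg in a single infusion needs a dose of 30/0.10 = 300 IU/kg at a 10% jump. At 60 IU/kg, the top of the recommended initial bleed doses, it would need a jump of 30/60 = 50%. For single infusions that rule is practically untouched.

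**The case against.** The case for leaving the rule alone has several parts.

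- **IU tables are planned.** SAP section 13 has weight-free tables for ITI (14.2.8), prophylaxis (14.2.17.1) and on-demand treatment (14.2.22.1). A reader might infer that every consumption figure is distorted; the documents show otherwise. This stands.
- **Mean dose/ED has no stated unit.** A reader might infer that this factor is biased in the inhibitor models. The SAP does not say that it is per kg, so this cannot be claimed. This stands. Weight and age are also in the factor list and may absorb part of an age-related error.
- **Long gaps are not the norm.** A reader might take the 3-monthly figures as typical. At the planned visit spacing the error is usually a few percent. This stands, although protocol section 6.1.2 expressly provides for children who need no study drug between 3-monthly visits in the first year, so long gaps before ED1 can occur.
- **The ED1 estimate may serve another purpose.** It could be meant as a baseline characteristic, and it could be carried forward. In either case there is no jump. This stands: the jump is one reading of an open text, not a demonstrated error.
- **Some infusions have a current weight.** Weight is taken within 12 hours before surgery and at visits where study drug may be given. Those infusions are not affected.
- **Carry-forward is prespecified, the analysis is exploratory, and the interim analysis has been run.** All true. These lower the severity and add a small cost to a change, but they do not remove a bias with a known sign.

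**Conclusion.** The point holds and is minor. For an infusion without a same-day weight, in a child who is gaining weight, the carry-forward rule overstates IU/kg. With growth of 1-10% per month, the mean overstatement is about 0.4-4.5% at gaps of 24-28 days. With 3-monthly weights only, the mean is 1.5-16% and the maximum 3-33%. The direction rests on weight rising between visits and the size on the growth rate, and both are assumptions.

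The error reaches the IU/kg tables and the part of the peak-treatment definition that depends on dose above 50 IU/kg; the other part, dosing on three or more successive days, does not use weight. It reaches mean dose/ED only if that is expressed per kg.

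A reader might go further and infer that the primary result is at risk. It is not: inhibitor incidence rests on titres and bleeding rates on counts and time, and neither uses weight.

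Whether IU/kg rises falsely from ED1 to ED2 depends on two things that the SAP does not state: whether the ED1 estimate is used for dose per kg, and whether it is carried forward.

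**What to change.** In SAP section 6.4.2, replace the general rule for dose per kg. For each infusion date without a measured weight, interpolate linearly between the nearest measured weights before and after; carry forward only after the last measured weight. Apply this to all IU/kg outputs and to the classification of prophylactic doses above 50 IU/kg. State the unit of mean dose/ED, and if it is per kg apply the same rule. With one rule for all dates, the open question about the ED1 estimate disappears.

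Record this as a change from protocol section 9.2.6, which specifies carry-forward for dose per kg.

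The cost is small but not nil. No new data are needed, and the ED1 calculation is extended to other dates. The price is a documented departure from the protocol rule and slightly reduced comparability with the interim IU/kg tables. Keeping the carry-forward version as a sensitivity analysis meets both. Linear interpolation carries its own error under compound growth, but a much smaller one: at 10% per month, with weights 91 days before and 28 days after ED1, it puts the ED1 weight 1.2% too high, against an apparent ED1-to-ED2 rise of 34.6% under carry-forward.

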4.4 Study Assessments

For assessments directly related to the evaluation of the primary and secondary endpoints, please refer to section 3.4 (Assessment of Objectives).

The following parameters will be assessed to allow a meaningful characterisation of the study population and to collect background information required for medical evaluation of study events:

- Subject demographics and baseline characteristics:
including ethnicity, age, height, weight, family history of haemophilia and inhibitors against FVIII.
- F8 gene mutation analysis including null/non-null specification
- Immunogenotyping
(HLA-typing, immune response gene profiling, F8 ethnic haplotype determination)
- RNA expression analysis
- FVIII level and recovery determination
- Half-life determination for patients under ITI treatment

- Medical History
- Concomitant Medication will be recorded throughout the trial
- Physical examinations will be performed at screening, at six monthly visits and at the completion visit.

5 **STUDY POPULATIONS**

5.1 **Subject Disposition**

For the analysis of this study the following populations will be considered:

- **Safety analysis population**: All subjects who received at least one dose of *Human-cl rhFVIII*
- **Intent to Treat (ITT) analysis population**: All subjects in the safety analysis population for whom any data was collected post treatment with *Human-cl rhFVIII*

Subpopulations of the ITT population will be

- Subjects of each ethnic group
 - Subjects with ITI treatment
 - Subjects with breakthrough bleedings, if appropriate
 - Subjects with surgical interventions, if appropriate
 - Subpopulations especially for inhibitor incidence analysis:
 - Subjects with different F8 gene mutations
 - Subjects with/without family history of inhibitors
 - Subjects by classes of EDs prior to inhibitor generation (1-5, 6-10, 11-20, 21-50, > 50)
 - Subject's age at first exposure (< 1, 1-6, > 6-12, > 12 months)
 - Subjects by reason for treatment prior to inhibitor generation
 - Subjects by intensity of treatment with/without peak treatment moments before inhibitor appearance (peak treatment moments defined as
 - ≥ 3 subsequent days with FVIII dosing, and/or
 - at least one day with prophylactic doses of > 50 IU FVIII /kg BW)
 - ED50 sub-population: Patients in the ITT population with at least 50 EDs of treatment with *Human-cl rhFVIII*
 - ED20 sub-population: Patients in the ITT population with at least 20 EDs of treatment with *Human-cl rhFVIII*.

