7 DEMOGRAPHICS AND BASELINE CHARACTERISTICS

The following demographic data will be collected:

- Birth date (Age) or at least month and year, Ethnic origin; “male” will be the standard value for Sex in the CRF.
Age will be calculated from the month and year of birth and the start of the first IMP administration.

Further baseline characteristics are:

- Height, Weight; Body Mass Index (BMI) which will be calculated from height and weight
- FVIII activity (%), FVIII antibody and Bethesda assay result (BU) (both assays) at screening
- Previous and concomitant medications
- Medical history and physical examination
- Underlying F8 gene defect including null/non-null mutation analysis (blood samples collected by the Investigator and analysis performed by a central laboratory)
- Family history of haemophilia and inhibitors against FVIII

All these demographic data and baseline characteristics will be presented in summary and/or frequency tables according to section 6.1 and as listed in section 13.

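### The SAP leaves open whose age rests on an assumed birth day of 1, a rule that can only overstate age, while the youngest age class is one month wide

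*SAP*

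**What the plan says.** Three parts of the SAP bear on this.

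- **SAP 6.4.2 (Handling of Dropouts or Missing Data)** covers age "calculations at screening and at ED1 in case of partially missing data". With month and year known, 1 "for day will be imputed". Two further bullets carry the same condition, "If month missing, but year available"; one supplies July and the other the first of July. A separate line reads "Date of birth: only month and year will be presented in listings". That line governs what is displayed and does not say that the day goes uncollected.
- **SAP 7 (Demographics and Baseline Characteristics)** gives the item collected as "Birth date (Age) or at least month and year". It then states: "Age will be calculated from the month and year of birth and the start of the first IMP administration". This sentence is not limited to incomplete dates.
- **SAP 5.1 (Subject Disposition)** defines subpopulations for inhibitor incidence, including "Subject's age at first exposure (< 1, 1-6, > 6-12, > 12 months".

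Age at first treatment is then a subgroup in the planned inhibitor incidence table with 95% confidence intervals (SAP 13, table 14.2.1.1). Age and age at first treatment are also candidate factors in the logistic and Cox regressions (SAP 9.1). Protocol 4.1 sets no age limit but expects a population mostly in the neonatal period or infancy.

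The SAP has no rule for an imputed birth date that falls after screening or first exposure.

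**The concern.** The two age rules differ in scope. SAP 6.4.2 fills in a day only when it is missing. Read literally, SAP 7 discards the day for everyone, and the only way the SAP offers to turn a month and year into a date is day 1. A programmer could follow either section and obtain different ages.

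The choice of day 1 also matters. It is the earliest possible birth date in the month, so the error goes one way and does not average out. In an adult trial a two-week shift would be trivial. Here the youngest class is one month wide, which is about the largest error the rule can make. At stake is the allocation of patients to age classes in a planned subgroup display of the primary endpoint.

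**Working it through.** The documents state no figure to reproduce, so the size of the error was derived.

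**Inputs.** From the SAP: the day-1 and July rules (6.4.2) and the class limits of 1, 6 and 12 months (5.1). Assumed: birth dates even over the calendar, and age at first exposure even within each class, varied for the youngest. All 1,461 birth dates of four calendar years were crossed with each true age in whole days, and simple formulas were used as a check.

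**1. Error from day 1.** The overstatement is birth day minus 1, so it runs from 0 to 30 days. With a mean month of 365.25/12 = 30.44 days, the mean is about (30.44 − 1)/2 = 14.7 days; enumeration also gives 14.7. Patients born on the 1st (48/1,461 = 3.3%) have no error. Nobody is made younger.

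**2. Youngest class.** A patient of true age *a* days leaves the class when *a* plus the overstatement reaches one month, so the chance is about *a*/30.4. The average over 0 to 30.4 days is 15.2/30.4 = 50%. Enumeration in whole days gives 47.5% with months taken as days/30.44, and 48.3% with completed calendar months. The result depends on when in the month first exposure occurs:

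| True age at first exposure | Mean *a*/30.4 | Enumerated share moved to 1-6 months |
|---|---|---|
| days 0-7 | 3.5/30.4 = 12% | 10-12% |
| days 0-14 | 7/30.4 = 23% | 21-23% |
| days 0-30 | 15/30.4 = 49% | 47.5-48.3% |
| days 14-30 | 22/30.4 = 72% | 70-71% |
| days 21-30 | 25.5/30.4 = 84% | 82-83% |

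**3. Older classes.** Only patients in the last month before a limit can cross it, and about half of them do. For 1-6 months that is 0.5 × 1/5 = 10% of the class (enumerated 9.7%). For >6-12 months it is 0.5 × 1/6 = 8.3% (enumerated 8.0%).

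**4. Day 15 for comparison.** The error is birth day minus 15, from −14 to +16 days. In units of a month, with age and birth day both uniform on 0 to 1, a patient moves up when their sum exceeds 1.5. That probability is 0.5²/2 = 12.5% (enumerated 13.5%). Without a cap, 11.1% of the youngest class would get a negative age. Capping the imputed birth date at screening or first dose removes these and leaves the 13.5% unchanged, because a capped date is never before the true birth date.

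**5. July rule.** With 1 July of the birth year, the error runs from −182 to +183 days. The age is negative when a child born before July is seen before 1 July of that year. For true age *a* in months below 6, the probability is (6 − *a*)/12: 5/12 = 42% at 1 month (enumerated 41%), 3/12 = 25% at 3 months (25%), 1/12 = 8% at 5 months (8%), and 0 from about 6 months.

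All these shares apply only to patients whose birth day, or month, is not used. The documents do not give that number.

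**The case against.** The strongest reply is that SAP 6.4.2 limits the day-1 rule to incomplete dates, and SAP 7 expects a full date with month and year as the fallback. On that reading a known birth day is used and few patients may be affected. This stands as a limit on scope: a reader might infer that every infant's age is overstated, and the documents do not support that. It would follow only if the unconditional sentence in SAP 7 governs, and even then infants born on the 1st have no error. The reply does not remove that sentence, so the conflict remains.

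Further objections, and what stands of each:

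- **The share of one half is an assumption.** Correct; it must be read with its range of about 10% to 83%.
- **The July branch should hardly arise**, since at least month and year are to be collected, and a negative age would show up in data checks. Correct; it is a flaw in a fallback and not an expected feature of the data.
- **The regressions barely suffer.** Largely correct for age as a continuous covariate. If day 1 were used for everyone, the common shift would go into the intercept or baseline hazard, leaving noise with SD about 30.4/√12 = 8.8 days. If the SD of age were 90 to 180 days (assumed; not in the documents), attenuation would be about 8.8²/(90² + 8.8²) = 0.9% down to 8.8²/(180² + 8.8²) = 0.2%. Age in classes is not protected in this way.
- **The analyses are exploratory** (SAP 6.4). True, and it limits the importance of the point. A descriptive table should still place patients in the right rows.

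**Conclusion.** The point holds as a conflict between SAP 6.4.2 and SAP 7, combined with an imputation rule poorly suited to infants. Where the birth day is not used, age is overstated by 0 to 30 days, about 15 on average. With age at first exposure even over the first month, about half of the affected patients truly under 1 month would be reported in the 1-6 month class. About 10% of the 1-6 month class and 8% of the >6-12 month class would also move up. If the month is missing too, which should be rare, about a quarter of infants truly aged 3 months would get a negative age.

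The consequence is confined to the age-at-first-exposure breakdown of inhibitor incidence, with a slight effect on regressions that use continuous age. Two stronger conclusions do not follow. The youngest class is thinned, not emptied: about half would remain under the even-spread assumption. Overall inhibitor incidence does not use age and is unaffected.

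**What to change.** Reconcile SAP 6.4.2 and SAP 7 with one rule:

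1. Calculate age from the full birth date wherever it was collected; showing only month and year remains a listing convention.
2. If the day is missing, impute day 15. If that falls after screening or first dose, use the earlier of those two dates as the birth date.
3. If the month is missing, set the age class to missing and drop the July imputation. This also removes the two bullets that share one condition.

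Step 1 removes the error for every patient with a recorded day. Step 2 still moves about 13% of affected patients in the youngest class up, against about half with day 1 under the same assumption, and its error no longer runs in one direction only. The cost is a few lines of SAP text and code, plus a missing age class for any patient without a birth month. No new data are needed. This is a cheap improvement.
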